3.0 STUDY REFERENCE INFORMATION

3.1 List of Abbreviations

 λ_z terminal elimination rate constant

AE adverse event

ALT alanine aminotransferase ANOVA analysis of variance

aPTT activated partial thromboplastin time

AST aspartate aminotransferase

AUC area under the plasma concentration-time curve

AUC₆ area under the plasma concentration-time curve from time 0 to 6 hours AUC_{∞} area under the plasma concentration-time curve from time 0 to infinity

AUCt area under the plasma concentration-time curve from time 0 to the last quantifiable

concentration

BCRP breast cancer resistance protein

BMI body mass index

CGI Clinical Global Impression Scale

CL/F apparent clearance

cm centimeter

C_{max} maximum observed plasma concentration

CNS central nervous system
CS clinically significant
D2 dopamine receptor, type 2

EC₅₀ half maximal effective concentration

ECG electrocardiogram

eCRF electronic case report form
EMA European Medicines Agency
FDA Food and Drug Administration
FSH follicle-stimulating hormone
GCP Good Clinical Practice
GGT γ-glutamyl transferase
GPR G-protein coupled receptor

h hour(s)

hCG human chorionic gonadotropin

ICF informed consent form

ICH International Council on Harmonisation

IEC independent ethics committee
INR international normalized ratio
IRB institutional review board

K₂EDTA dipotassium ethylenediamine tetraacetic acid

LFT liver function test

Study No. CVN424-201 Page 17 of 73

Protocol v. 4.0 14 July 2021

m meter

MedDRA Medical Dictionary for Regulatory Activities

mg milligram

MSN medium spiny neuron

N number

NCS not clinically significant

ng nanogram

Occ₅₀ 50% receptor occupancy
Occ₉₀ 90% receptor occupancy
PD Parkinson's disease

PGI Patient Global Impression Scale

Pgp P-glycoprotein 1
PK pharmacokinetic
PTE pretreatment event

QD once daily

OATP organic-anion-transporting polypeptide
QTcB QT interval with Bazett's correction method
QTcF QT interval with Fridericia's correction method
QUIP Questionnaire for Impulsive-Compulsive Disorders

RNA ribonucleic acid
RO receptor occupancy
SAE serious adverse event
SAP statistical analysis plan
SD standard deviation

SUSARs suspected unexpected serious adverse reactions

 $t_{1/2z}$ terminal elimination half-life TEAE treatment-emergent adverse event

 $\begin{array}{ll} t_{max} & & time \ to \ reach \ C_{max} \\ ULN & upper \ limit \ of \ normal \end{array}$

UPDRS Unified Parkinson's Disease Rating Scale

 V_z /F apparent volume of distribution WOCBP women of childbearing potential

Study No. CVN424-201 Page 18 of 73

Protocol v. 4.0 14 July 2021

4.0 INTRODUCTION

4.1 Background

Parkinson's disease (PD) is a progressive neurodegenerative disorder of the central nervous system (CNS) caused by the gradual loss of the dopaminergic neurons of the substantia nigra pars compacta that project to the striatum (Wichmann, 2011). PD afflicts >1 million individuals in the United States of America and >10 million worldwide (APDA.org, accessed 26 Jan 2018), causing cardinal symptoms of tremor, bradykinesia, and postural instability. The financial burden of PD is significant.

GPR6 is an orphan G-protein coupled receptor that is selectively expressed in the brain, and is a nondopaminergic target for the treatment of PD. In the brain, GPR6 is predominantly localized to striatopallidal medium spiny neurons (MSNs) that also express dopamine D2 receptors (Lein et al. 2007; also Cerevance data on file). GPR6 is a constitutively active G_s- coupled receptor that functionally opposes the G_i-coupled D2 receptor in indirect MSNs. Pharmacological intervention to inhibit the GPR6 pathway using an inverse agonist is predicted to exert antiparkinsonian effects by reducing overactivity of striatopallidal output neurons in the indirect pathway without activating the dopamine D1-receptor expressing MSNs of the direct (striatonigral) pathway.

CVN424 is a potent and selective inverse agonist of GPR6. The efficacy of CVN424 has not previously been studied in humans, but has been demonstrated in various animal models of PD. It was dose-dependently effective as monotherapy in reversing immobility in rats with bilateral 6-OHDA lesions. It dose-dependently blocked D2 antagonist induced (indirect pathway dependent) catalepsy in rats. Safety studies of CVN424 conducted in rodents, dogs, and monkeys have demonstrated minimal toxicity, with the primary dose-limiting effect of body weight loss or reduced body weight gain. All toxicity findings demonstrated dose-dependency and reversibility of effects.

A first-in-humans safety study of CVN424 in 64 healthy volunteers has been completed (NCT03657030); the study findings are summarized in the Investigator's Brochure. In brief, CVN424 was safe and well tolerated when administered to healthy subjects as a single oral dose of between 1 mg and 225 mg, or when administered as 7 daily oral doses of between 25 mg and 150 mg. Study drug-related adverse events (AEs) were reported by 2 of 40 subjects (5.0%) overall in the single-dose cohorts (feeling hot; headache). Study drug-related AEs were reported by 2 of 24 subjects (8.3%) overall in the multiple-dose cohorts (dysphagia; chills). With one exception, all AEs were mild in severity; dysphagia of moderate severity led to treatment discontinuation in one subject after their third daily dose (75 mg). There were no severe or serious AEs, and all AEs had resolved by the end of the study. Administration of the first dose of CVN424 was associated with an elevation in group mean and median body temperature. These changes were detectable at 1 h post-dose (the earliest scheduled post-dose assessment), increased further by 6 h post-dose, and spontaneously returned to baseline by 24 h post-dose. The increases tended to be larger at higher doses but did not appear to be strictly dose-proportional. A trend of increase in heart rate while standing was also observed with a similar time course and relationship to dosage. These trends were not considered clinically significant, and no individual vital sign measurement was reported as an AE. In the multiple-dose cohorts, elevations in body temperature and heart rate were observed only after the first dose of CVN424, not following subsequent doses. No other trends in vital sign measurements

Study No. CVN424-201 Page 19 of 73

Protocol v. 4.0 14 July 2021

were noted. No treatment-related trends were observed in the clinical laboratory results or 12-lead electrocardiogram (ECG) measurements.

In the healthy volunteer study, CVN424 in suspension was rapidly absorbed after oral administration in the fasted state; peak plasma concentration was usually attained between 1 and 3 h post-dose (median 1.5 h). When CVN424 was administered after a meal, the peak plasma concentration was delayed and decreased while total exposure was minimally increased compared to the same dose level administered under fasted conditions. With repeated once-daily dosing, trough plasma concentrations usually reached a steady-state level by Day 4, with a terminal elimination half-life of approximately 33 h. Accordingly, CVN424 PK is appropriate for once-daily oral dosing, with or without food.

CVN424 is expected to be a pharmacological treatment for PD subjects, as monotherapy or adjunctive to dopaminergic therapy, to elicit sustained improvement of motor activity with a reduced risk of troublesome dyskinesia compared with dopaminergic therapies. As a novel, first in class, non-dopaminergic drug for the symptomatic treatment of PD, CVN424 may become a significant addition to neurologists' clinical armamentarium.

4.2 Rationale for the Proposed Study

Although available medications and implanted deep brain stimulation can often treat the motoric symptoms of PD, many patients with PD have motor fluctuations despite treatment and may not experience improvement in non-motor symptoms. Moreover, current treatments are fraught with side-effects (e.g., drug induced dyskinesia), and their efficacy diminishes as the disease progresses. Therefore, novel therapies are needed to improve the quality of life for patients with PD. The efficacy of CVN424 in animal models of PD supports its investigational use in PD patients.

A safety and pharmacokinetic (PK) study previously performed in 64 healthy volunteers supports the selected dose levels of CVN424 in this study. Section 6.2 outlines the justification for the planned dosages. This will be the first study conducted with CVN424 in patients with PD, and will examine the safety, tolerability, efficacy, and plasma PK of the compound in PD patients.

Study No. CVN424-201 Page 20 of 73

Protocol v. 4.0 14 July 2021

5.0 STUDY OBJECTIVES AND ENDPOINTS

5.1 Objectives

5.1.1 Primary Objective

To assess the safety and tolerability of CVN424 when administered as daily oral doses for 28 days, adjunctive to levodopa, in subjects with Parkinson's disease and motor fluctuations.

5.1.2 Secondary Objectives

- To assess potential efficacy of CVN424 adjunctive to levodopa in alleviating symptoms of PD
- To assess CVN424 multiple-dose PK in blood of PD subjects

5.1.3 Exploratory Objectives

 To explore possible serum/plasma, DNA and/or ribonucleic acid (RNA) markers (e.g., drug metabolic enzyme and transporter polymorphisms) that may contribute to variability in CVN424 PK, pharmacodynamics, safety or efficacy

5.2 Endpoints

5.2.1 Primary Endpoints

The primary endpoint of this study will be:

Percentage of subjects with treatment-emergent adverse events (TEAE) related to study drug

5.2.2 Secondary Endpoints

The secondary endpoints will include:

- Percentages of subjects with abnormal and clinically significant (CS) safety laboratory test results, ECG test results, or vital sign measurements at least once post-dose
- Change from baseline in 2-day average OFF time at Day 27 as recorded in the Patient Motor Diary

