9.1.7 Documentation of Concurrent Medical Conditions

Concurrent medical conditions are those significant ongoing conditions or diseases that are present at signing of ICF. This includes CS laboratory, ECG, or physical examination abnormalities noted at Screening examination. The condition (i.e., diagnosis) should be described.

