All CS laboratory abnormalities must be recorded as a PTE/AE in the subject's source documents and on the appropriate eCRF. A CS laboratory abnormality that has been verified by retesting will be followed until the abnormality returns to an acceptable level or a satisfactory explanation has been obtained.

⁽a) Serum hCG pregnancy test will be done at Screening in women subjects.

⁽b) FSH level will be obtained for female subjects at Screening if they are postmenopausal (i.e., last regular menstrual cycle >2 years) and not surgically sterile. The result must be >40 IU/L for the subject to be enrolled.

Study No. CVN424-201 Page 37 of 73

Protocol v. 4.0 14 July 2021

If subjects experience ALT or AST >3 ×ULN, follow-up laboratory tests (at a minimum, serum alkaline phosphatase, ALT, AST, total bilirubin, GGT, and INR) should be performed within a maximum of 7 days and preferably within 48 to 72 h after the abnormality was found.

(Please refer to Section 7.4 for discontinuation criteria, and Section 9.6.3 for the appropriate guidance on Reporting of Abnormal LFT in relation to ALT or AST >3 ×ULN in conjunction with total bilirubin >2 ×ULN).

If the ALT or AST remains elevated >3 ×ULN on these 2 consecutive occasions, the investigator must contact the Medical Monitor for consideration of additional testing, close monitoring, possible discontinuation of study medication, discussion of the relevant subject details and possible alternative etiologies. The abnormality should be recorded as an AE (please refer to Section 9.6.3 Reporting of Abnormal LFT for reporting requirements).

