9.5.3 Additional Points to Consider for PTEs and AEs

An untoward finding generally may:

- Indicate a new diagnosis or unexpected worsening of a pre-existing condition. (Intermittent events for pre-existing conditions underlying disease should not be considered PTEs or AEs)
- Necessitate therapeutic intervention
- Require an invasive diagnostic procedure
- Require discontinuation or a change in dose of study medication or a concomitant medication
- Be considered unfavorable by the investigator for any reason
- PTEs/AEs caused by a study procedure (e.g., a bruise after blood draw) should be recorded as a PTE/AE

Diagnoses vs signs and symptoms:

• Each event should be recorded to represent a single diagnosis. Accompanying signs (including abnormal laboratory values or ECG findings) or symptoms should NOT be recorded as additional AEs. If a diagnosis is unknown, sign(s) or symptom(s) should be recorded appropriately as a PTE(s) or as an AE(s)

Laboratory values and ECG findings:

Changes in laboratory values or ECG parameters are only considered to be PTEs or AEs if they
are judged to be CS (i.e., if some action or intervention is required). A laboratory re-test and/or
continued monitoring of an abnormal value are not considered an intervention. In addition,
repeated or additional noninvasive testing for verification, evaluation or monitoring of an
abnormality is not considered an intervention

Study No. CVN424-201 Page 47 of 73

Protocol v. 4.0 14 July 2021

• If abnormal laboratory values or ECG findings are the result of pathology for which there is an overall diagnosis (e.g., increased creatinine in renal failure), the diagnosis only should be reported appropriately as a PTE or as an AE

Pre-existing conditions:

- Pre-existing conditions (present at the time of signing of the ICF) are considered concurrent medical conditions and should NOT be recorded as PTEs or AEs. Baseline evaluations (e.g., laboratory tests, ECG, X-rays etc.) should NOT be recorded as PTEs unless related to study procedures. However, if the subject experiences a worsening or complication of such a concurrent condition, the worsening or complication should be recorded appropriately as a PTE (worsening or complication occurs before start of study medication) or an AE (worsening or complication occurs after start of study medication). Investigators should ensure that the event term recorded captures the change in the condition (e.g., "worsening of...")

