12.1.4.2 Clinical Laboratory Evaluation

Individual results of laboratory tests from hematology, chemistry, urinalysis, and endocrine panels that are abnormal and CS will be summarized and listed. Observed values and change from baseline to post-dose laboratory data will be summarized for placebo, each CVN424 dose level and CVN424 overall. All clinical laboratory data will be listed.

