12.1.4.3 Vital Signs

Individual results of vital signs that are abnormal and CS will be summarized and listed. Observed values and changes from Baseline in vital sign measurements will be summarized by placebo, each CVN424 dose level and CVN424 overall. All vital sign data will be provided in the data listings.

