- (b) Vital signs (oral temperature, respiration, heart rate, and blood pressure) and weight will be recorded at Screening, Baseline, Day 1, and at subsequent Study Visits. On Day 1 and Day 8, the assessments will be conducted pre-dose [within 90 minutes prior to dosing], and at least hourly through 3 h post-dose. Triplicate orthostatic vital signs (blood pressure and heart rate) will be recorded 15 minutes apart at baseline. Orthostatic vital signs (non-triplicate) will be recorded pre-dose and at 3 h post-dose on Days 1 and 8. Orthostatic vital signs will be measured after at least 5 minutes supine and again at 2 minutes after standing at each scheduled orthostatic timepoint.
- (c) Clinical laboratory tests (hematology, serum chemistry, urinalysis, and endocrine) will be collected at Screening, Baseline, Day 8, Day 27, Day 35, and Early Termination (if applicable) visits. Urine hCG pregnancy test will be performed on female subjects of childbearing potential on Day 1 prior to dosing.
- (d) Screening laboratory testing will include all items included under 'Clinical Laboratory Tests" plus urine drug & cotinine screen, and for female subjects a serum pregnancy test (hCG). An FSH level will be obtained on post-menopausal women (defined as continuous amenorrhea of at least 2 years and not surgically sterile). One additional tube for plasma and one for serum will be collected for archiving (frozen storage) to support potential post hoc laboratory testing.
- (e) Subjects will receive standardized instruction in how to complete the Patient Motor Diary (Hauser diary). After training, subjects who have passed initial Screening procedures will complete Patient Motor Diary entries for 4 consecutive 30-minute periods during a screening visit while observed and scored by a skilled rater. The concordance testing session must include at least one ON and one OFF period; the test session will extend for up to 4 additional 30 min. periods until there is at least one in each state. Concordance must be within 75% for subject eligibility.
 - Following a successful concordance test and prior to randomization, subjects must complete the Patient Motor Diary at home over 48 h and demonstrate both an acceptable quality of the diary, with no more than 4 errors per day, and average daily OFF time of at least 2 h and not one day below 1.0 h.

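### The secondary safety endpoint counts post-dose clinically significant results without requiring that they be new since baseline, which dilutes and adds noise to the comparison between arms

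*Combined protocol and SAP*

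**What the plan says.** The endpoint in Section 5.2.2, worded the same way in Section 2.0, is "Percentages of subjects with abnormal and clinically significant (CS) safety laboratory test results, ECG test results, or vital sign measurements at least once post-dose". The analysis text adds no baseline condition. For laboratory data, Section 12.1.4.2 refers to results from "panels that are abnormal and CS will be summarized and listed". For vital signs, Section 12.1.4.3 says "Individual results of vital signs that are abnormal and CS will be summarized and listed". Section 12.1.4.4 treats ECGs in the same way and makes shift tables optional, for ECG interpretations only.

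The plan expects some subjects to have such findings before dosing. Section 9.1.7, on concurrent medical conditions, says "This includes CS laboratory, ECG, or physical examination abnormalities noted at Screening examination".

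Elsewhere the plan does refer to baseline. Section 9.1.3 judges physical findings as changes from the baseline examination. Under Section 9.5.3, conditions present at consent "are considered concurrent medical conditions and should NOT be recorded as PTEs or AEs", unless they worsen. Section 12.1.4.2 also commits to group summaries: "Observed values and change from baseline to post-dose laboratory data will be summarized for placebo, each CVN424 dose level and CVN424 overall". Sections 12.1.4.3 and 12.1.4.4 make the same commitment for vital signs and ECGs.

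On recording, Section 9.1.8 says "All CS laboratory abnormalities must be recorded as a PTE/AE" and makes no exception for abnormalities already present at consent or Screening.

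**The concern.** A safety endpoint in a placebo-controlled trial should count what happens after treatment starts. As worded, this one counts what is present after treatment starts, whenever it began. A subject whose laboratory value or ECG was graded CS before the first dose, and is graded CS again at any later visit, is scored exactly like a subject who developed the abnormality on treatment.

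A single post-dose CS grade is enough, and Appendix A gives a persisting abnormality several chances to be scored: three laboratory visits (Days 8, 27 and 35), five ECG timepoints and at least eleven vital-sign timepoints.

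At stake is the clarity of this one comparison. Pre-existing cases raise the percentage in every arm, shrink the apparent difference and ratio, and add variation unrelated to the drug.

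**Working it through.** **No figure to reproduce.** The plan states no expected rate, test or power for this endpoint, and its summaries are descriptive. What follows is an illustration.

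**Inputs.** n = 45 per arm (Section 12.3). b is the share of subjects with a CS abnormality before dosing that is graded CS again after dosing. The documents do not give it, so 2%, 5% and 10% are assumed. q is the true rate of new CS abnormality, also assumed.

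**Step 1: what the endpoint measures.** Reported rate = b + (1 − b)q. With the same b in both arms, the difference is (1 − b)(q_active − q_placebo). If only a fraction r of baseline abnormalities is graded CS again, b is replaced by (baseline prevalence × r).

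Small example: true rates of 5% and 0%, with b = 10%.
- Active: 1 − 0.90 × 0.95 = 14.5%.
- Placebo: 10.0%.
- The difference falls from 5.0 to 4.5 points.

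**Step 2: noise from pre-existing cases alone.** Expected count per arm = 45b. SD of the between-arm difference = √[2b(1 − b)/45].

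| b | Cases per arm | SD of difference |
|---|---|---|
| 2% | 0.9 | √(0.0392/45) = 3.0 points |
| 5% | 2.3 | √(0.095/45) = 4.6 points |
| 10% | 4.5 | √(0.18/45) = 6.3 points |

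Table 3 in Section 8.1.3 lists 40 per arm. Dividing by 40 instead gives 3.1, 4.9 and 6.7 points, so the choice matters little.

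**Step 3: a larger assumed effect.** New-abnormality rates of 5% (placebo) and 20% (active) are assumed. Power is Φ[(d − 1.96·SE₀)/SE₁], with d the difference, SE₀ the pooled and SE₁ the unpooled standard error, at two-sided 0.05. No such test is planned; power serves only as a yardstick.

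| b | Placebo | Active | Difference | Ratio | Power as written | Power, new cases only |
|---|---|---|---|---|---|---|
| 0 | 5.0% | 20.0% | 15.0 points | 4.0 | 0.58 | 0.58 |
| 5% | 9.8% | 24.0% | 14.3 points | 2.5 | 0.44 | 0.56 |
| 10% | 14.5% | 28.0% | 13.5 points | 1.9 | 0.35 | 0.53 |

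The last column uses only the 45(1 − b) subjects per arm without a baseline abnormality. At b = 2% the difference is 15.0 × 0.98 = 14.7 points. If 10% have a baseline abnormality and half are graded CS again, the b = 5% row applies.

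**Step 4: are the data there?** Appendix A says laboratory tests "will be collected at Screening, Baseline, Day 8, Day 27, Day 35". ECGs are taken at Screening and before dosing on Day 1. Vital signs are taken at Screening, at Baseline and before dosing on Day 1. A pre-dose reference therefore exists for all three.

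**The case against.** The strongest reply is that b should be small. Section 9.5.3 treats a laboratory or ECG change as CS only when something has to be done about it, and excludes retesting and monitoring. A stable, known abnormality would often not be graded CS again. Section 7.2 excludes subjects with out-of-range supine blood pressure or heart rate at Screening, symptomatic orthostatic hypotension, or a CS disorder that the investigator expects to confound the results. This largely stands and is why the lower values of b are the more plausible. It does not remove the point: the definition in Section 9.5.3 does not mention vital signs, no comparable laboratory or ECG limits appear in Section 7.2, and Section 9.1.7 still provides for CS findings at Screening.

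A second reply is that Section 12.1 leaves further definition of analysis variables to a SAP finalised before unblinding. That is so. The supplied document contains no separate SAP text, so whether a newness rule was added cannot be seen.

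Two stronger readings are tempting, and the documents support neither.
- A reader might infer that the endpoint could conceal a drug effect or leave the safety objective unanswered. Randomisation balances pre-existing cases in expectation, the difference shrinks only by (1 − b), and other baseline-referenced safety analyses are required.
- A reader might infer from Section 9.1.8 that persisting abnormalities inflate the TEAE count. Section 2.0, Section 12.1.4.1 and Appendix A note (m) classify events by onset or exacerbation relative to dosing, so an unchanged pre-dose abnormality should not become a TEAE.

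**Conclusion.** The concern holds for this endpoint as worded. Pre-existing abnormalities graded CS again after dosing count as outcomes in every arm. The absolute difference loses a fraction b of its size. The relative loss in the ratio is larger, and chance imbalance adds an SD of 3.0 to 6.3 points for b from 2% to 10% with 45 per arm. All of this rests on assumed values of b, and the power figures also rest on assumed event rates and an assumed test.

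The result is dilution and noise without systematic bias. The primary endpoint (drug-related TEAEs, with the baseline rules of Section 9.5.3) and the required change-from-baseline summaries by arm are unaffected, so the safety evaluation as a whole stands. The endpoint should be tightened, but the flaw is not critical.

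The conflict between Section 9.1.8 and Sections 9.1.7 and 9.5.3 is a separate matter of consistent recording and adds nothing to the sizes above.

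**What to change.** In Sections 2.0 and 5.2.2, define the endpoint as the percentage of subjects with a post-dose abnormal and CS laboratory, ECG or vital-sign result for a parameter that was not CS at the last pre-dose assessment. Carry this into Sections 12.1.4.2 to 12.1.4.4. Tabulate CS status at baseline against post-dose CS status by arm for all three types of measure, and keep every CS result in the listings. Worsening of an already CS parameter stays captured through the AE rules in Section 9.5.3.

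Separately, reconcile Section 9.1.8 with Sections 9.1.7 and 9.5.3, so that sites record an abnormality present at consent or Screening in one way.

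**Cost.** No new visits or samples. Reported percentages may be lower, and a worsening of an already CS parameter will appear as an AE and in the listings instead of in this endpoint. Sections 9.1.8 and 9.1.11 already call for a significance grade on laboratory reports and ECGs. Section 9.1.5 names none for vital signs, although the endpoint presupposes one, so the eCRF should be checked for it before and after dosing. Adding an investigator judgement of worsening to the endpoint itself is not advised: the documents do not say that one is recorded for these measures, so it could need new eCRF fields and site instructions.
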